## **2.8 Key inclusion criteria**

Inclusion Criteria for all Participants:

- 1) Age 18-80, right-handed male or female, any race;
- 2) Absence of clinical dementia
- 3) English speaking
- 4) Blood pressure not exceeding 150/90 mmHg, treated or untreated
- 5) Normal result on liver-function test
- 6) No history of ulcer disease or GI bleeding
- 7) No renal insufficiency
- 8) Weight greater than 110 lbs

Additional Inclusion Criteria for Depressed Participants:

CONFIDENTIAL

- 1) DSM-IV criteria for MDD
- 2) PHQ-8 Score equal to or greater than 10

## **2.9 Key exclusion criteria**

Stress and Inflammation exclusions:

- 1) Known history of relevant severe drug allergy or hypersensitivity (e.g. to Citalopram or Escitalopram, and/or to celecoxib, aspirin, or other NSAIDs; known demonstration of allergic-type reactions to sulfonamides);
- 2) Does not speak English;
- 3) Cannot give informed consent;
- 4) MRI contraindications (e.g., foreign metallic implants, pacemaker);
- 5) Known primary neurological disorders, such as Parkinson's disease, Alzheimer's disease, traumatic brain injury, cognitive impairment or dementia,
- 6) Known severe inflammatory disease such as systemic lupus erythematosus, known autoimmune diseases, such as multiple sclerosis, rheumatoid arthritis;
- 7) Clinical Dementia Rating Scale score greater than 0;
- 8) Diagnosis of a chronic psychiatric illness other than MDD at the discretion of the study doctor;
- 9) Significant handicaps (e.g. uncorrected hearing or visual impairment, mental retardation) that would interfere with testing;
- 10) Bleeding diathesis;
- 11) Severe Medical problem, which in the opinion of the investigator would pose a safety risk to the subject;
- 12) Clinically significant cardiovascular disease that will be assessed on a case-by-case basis.  
Clinically significant cardiovascular disease usually includes one or more of the following: cardiac surgery or myocardial infarction within the last 4 weeks; unstable angina; acute decompensated congestive heart failure or class IV heart failure; current significant cardiac arrhythmia or conduction disturbance, particularly those resulting in ventricular fibrillation, or causing syncope or near syncope; uncontrolled high blood pressure; QTc greater than 450msec (by history for subjects with cardiac disease); documented prior stroke;
- 13) Clinically significant abnormalities on EKG. Primary AV block or Right bundle branch block are not necessarily exclusionary;
- 14) Current diagnosis of cancer
- 15) Current diagnosis of HIV, active Hepatitis B and/or Hepatitis C
- 16) Use of an Investigational medicine within the past 30 days;
- 17) Use of Coumadin, Warfarin within the past 2 months;
- 18) Current treatment with psychotropic drugs or drugs that affect the CNS such as beta-blockers, mood stabilizers, antipsychotics, steroids or non-steroidal anti-inflammatory medications or other antidepressants. No subjects will be included in the study unless

CONFIDENTIAL

they have been off all psychotropics for at least 3 weeks, except in the case of fluoxetine, where 5 weeks off treatment will be required;

- 19) Current alcohol or substance abuse disorder, schizophrenia or other psychotic disorder, bipolar disorder, or current OCD;
- 20) Abnormal liver-function test
- 21) Current diagnosis of ulcer disease, Chron's disease, GI bleeding or anemia
- 22) Weight less than 110 lbs
- 23) Renal insufficiency
- 24) Any other factor that in the investigator's judgment may affect patient safety or compliance (e.g. distance greater than 100 miles from this facility);

Additional Exclusion Criteria for Depressed Subjects:

- 1) Active suicidality or current suicidal risk as determined by the investigator

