- (8) Participants will be closely monitored for problems resulting from participation. They will be provided with contact information for research personnel should any problems or questions arise, and they will be contacted by research personnel during their participation to ascertain the presence of any problem.

Treatment Design:

CONFIDENTIAL

All subjects will have an initial telephone screening. Screened participants will have an appointment to come to the research facility to conduct informed consent for the diagnostic screen and blood test to measure CRP levels and test for HIV, Hepatitis B and C, autoimmune diseases and rheumatoid factor. This visit is expected to last approximately 90 minutes. Informed consent will be obtained, and then participants will undergo a blood draw to assess c-reactive protein level, as they will be stratified depending on the current level. Subjects will participate in a structured clinical interview, EKG, and a review of medical history with the research staff. All participants will be given the screener for Structured Clinical Interview for DSM-IV (SCID-1) to ascertain the presence or absence of Major Depressive Disorder (MDD) and to rule out other psychiatric disorders. They will also be given the Hamilton Rating Scale for (HAMD) and Montgomery-Asberg Depression Rating Scale (MADRS). Those with MDD may be enrolled in the experimental condition. Potential Controls may be enrolled in the control condition if they have no psychiatric disorders and their HAMD score is less than or equal to 7. Participants will receive an EKG to screen for any abnormalities or conditions that would suggest they should not receive medication thus be deemed ineligible at this point. Participants will be asked medical screening questions (e.g., from the Framingham Scale to determine a vascular risk factor), and they will be assessed with the Clinical Dementia Rating (CDR) scale to determine whether there is any cognitive impairment. At the screening, the participants will be asked to fill out the Perceived Stress Scale (PSS) and Life Events Stress (LES). A trained study team member will then perform a neuropsychiatric test on the participants that include questions about the participants' memory, attention, spatial abilities, general abilities, motor control, and problem solving.

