#### **10.1.6 Celecoxib**

Celecoxib has been associated with an increased risk of cardiovascular events in people with cardiovascular disease (Celecoxib package insert). Side effects include nausea, diarrhea, gas, cold symptoms, sore throat, lack of energy, loss of appetite, fever, rash, back pain, and flu-like symptoms, among others. Participants would be instructed to contact study members if severe,

CONFIDENTIAL

serious, or persisting side effects occur. There is a rare risk of stroke or heart attack; however these very serious side effects are greatest risk for those with current clinically significant cardiac disease, and we are excluding these people (clinically significant cardiovascular disease usually includes one or more of the following: cardiac surgery or myocardial infarction within the last 4 weeks; unstable angina; acute decompensated congestive heart failure or class IV heart failure; current significant cardiac arrhythmia or conduction disturbance, particularly those resulting in ventricular fibrillation, or causing syncope or near syncope; uncontrolled high blood pressure; QTc greater than 450msec (by history for subjects with cardiac disease); documented prior stroke; clinically significant abnormalities on EKG.) Celecoxib also has increased risk for gastrointestinal bleeding and hepatic impairment. We will exclude those with current ulcer disease or GI bleeding as well as those with liver function impairment (as determined by a liver function test prior to entry into the study). We are excluding clinically significant cardiovascular disease for the past 6 months.

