### **10.4 Risk Benefit Assessment**

There are risks associated with participation in this study, but they are minimal and even rare and it is believed that the benefits of conducting the study outweigh the minimal risk.

Celecoxib has been associated with an increased risk of cardiovascular events in people with cardiovascular disease. To mitigate this risk we will enforce our stringent exclusion criteria for people with cardiac risk factors, monitor blood pressure, assess gastrointestinal safety, appoint an independent data safety monitoring board (DSMB) and conduct this study under an FDA-IND for the use of celecoxib. A separate risk/benefit analysis for the use of celecoxib follows below.

CONFIDENTIAL

Because of these precautions, the addition of Celecoxib is not a greater than minimal risk to participants. We will perform the EKG and cardiac risk assessment following the completion of the initial phase of the study before entering into the celecoxib phase in case their cardiac profile has changed. Our exclusion criteria related to cardiac risk include: lifetime history of cardiac surgery or myocardial infarction; unstable angina; acute decompensated congestive heart failure or class IV heart failure; current significant cardiac arrhythmia or conduction disturbance, particularly those resulting in ventricular fibrillation, or causing syncope or near syncope; uncontrolled high blood pressure; QTc greater than 450msec (by history for subjects with cardiac disease); documented prior stroke; Clinically significant abnormalities on EKG.

Additionally, subjects will have blood pressure monitoring at each visit, as it may be a surrogate for celecoxib thrombotic risk. There is also a risk of boredom and/or fatigue from study visits. There is also a rare risk of breach of confidentiality. We have developed procedures for Protection Against or Minimizing Risks for the participant. To reduce risks to participants, only physicians and scientists with extensive training and experience will supervise and perform procedures. Participants will be closely monitored for any side effects from taking escitalopram. There are significant benefits to the research. This study has the potential to greatly increase our knowledge in the treatment and prevention of Depression. No direct benefits are expected to the participant aside from the satisfaction of participating in a study that addresses an important health issue.

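### The cardiovascular-history exclusion is stated four different ways, the Framingham limit is missing from the eligibility list, and the blood-pressure stopping rule can depend on a baseline measurement that is optional

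*Combined protocol and SAP*

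**What the plan says.** Section 2.9 item 12 excludes "Clinically significant cardiovascular disease that will be assessed on a case-by-case basis", and its examples of what this usually means include "cardiac surgery or myocardial infarction within the last 4 weeks". Section 10.1.6 repeats that list with the same window, then closes with "We are excluding clinically significant cardiovascular disease for the past 6 months". Section 10.4 puts it differently: "Our exclusion criteria related to cardiac risk include: lifetime history of cardiac surgery or myocardial infarction". Section 10.5.1 goes further and bars patients with any earlier cardiovascular disease, a term it leaves undefined.

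Section 10.5.1 also admits only patients with a Framingham score below 13, which it equates to a 15% ten-year risk. Sections 2.8 and 2.9 contain no such item. The score is collected: section 5.2 has screening questions "from the Framingham Scale to determine a vascular risk factor", and the flow-chart in 12.1 schedules it at the in-person screen. On blood pressure, section 2.8 requires "Blood pressure not exceeding 150/90 mmHg, treated or untreated".

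After listing its precautions, section 10.4 concludes: "Because of these precautions, the addition of Celecoxib is not a greater than minimal risk to participants".

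The stopping rule in section 10.5.2 has two parts, both required: a 10 mmHg rise in mean daytime and nighttime systolic pressure over the baseline ABPM, and a daytime mean systolic of at least 150 mmHg. The same section then makes ABPM optional and relies on office readings. If these are high (150 mmHg systolic or 90 mmHg diastolic) at two or more visits, a follow-up ABPM is arranged and judged by the same criteria.

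**The concern.** Celecoxib carries a cardiovascular hazard that the protocol itself sets out at length, so who is kept out and when dosing stops are its main protections. If sections differ on who is kept out, staff working from 2.8 and 2.9 may apply a looser rule than the one the IRB and DSMB read in section 10. The minimal-risk conclusion would then cite exclusions that nobody is required to apply.

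The stopping-rule problem is different in kind. The participant sent for a follow-up ABPM is the one with sustained raised readings. If no baseline recording was made, the change part of the rule cannot be evaluated, and a pre-treatment baseline cannot be obtained afterwards.

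**Working it through.** No power or sample-size arithmetic is involved. The check sets the statements side by side and works through the logic of the stopping rule.

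**History rule.** Test cases against each statement:

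| Patient | 2.9 item 12 and the 10.1.6 list (4 weeks) | 10.1.6, last sentence (6 months) | 10.4 (lifetime) | 10.5.1 (any past disease) |
|---|---|---|---|---|
| MI 3 months ago | outside the listed window; investigator's discretion | excluded, if the class includes MI | excluded | excluded |
| MI 2 years ago | outside the listed window; investigator's discretion | not excluded by this sentence | excluded | excluded |
| Treated hypertension within 150/90 mmHg, no event | admitted by 2.8 item 4 | not addressed | not excluded if controlled | depends on the undefined term |

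The first two patients get different answers in different sections, and no text says which section governs. In the third row, 10.5.1 can hardly mean to bar controlled hypertension, because 2.8 admits it and 10.5.2 says such patients may enrol. The other listed conditions (prior stroke, unstable angina, class IV failure, arrhythmia, QTc above 450 msec, uncontrolled hypertension) are common to 2.9, 10.1.6 and 10.4. The disagreement is therefore mainly about MI and cardiac surgery.

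**Framingham limit.** Section 10.5.1 reports a pilot mean score of 16.2 at ages 75 to 84. A depressed patient at that mean fails the limit of 13 in 10.5.1 but meets no exclusion on that ground in 2.8 or 2.9.

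**Stopping rule.** Let A be a rise of at least 10 mmHg over the baseline ABPM means, and B a follow-up daytime mean systolic of at least 150 mmHg. Stop if A and B both hold.

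| Baseline ABPM | Follow-up daytime mean | A | B | Decision |
|---|---|---|---|---|
| present | any | known | known | decided |
| absent | below 150 | unknown | false | not met, whatever A is |
| absent | 150 or more | unknown | true | equals A, so undecided |

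Only the last row fails. An example shows that A matters: with a baseline of 145 (day) and 130 (night) and a follow-up of 152 and 133, the rises are 152 − 145 = 7 and 133 − 130 = 3. Both are below 10, so the participant continues. Without the baseline, the same follow-up cannot be classified.

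**Is a baseline assured elsewhere?** No. Section 5.4 says participants may have ABPM. The flow-chart row that includes ABPM at baseline joins it to stool-blood and hematocrit testing with an and/or, so it does not override the explicit statement in 10.5.2.

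**Number affected.** This would need the number flagged by office readings, the share of them without a baseline ABPM, and the share with a daytime mean of at least 150 mmHg. For the history rule it would need the number of candidates with an older MI or cardiac surgery. The documents give none of these.

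**The case against.** Several points on the other side stand.

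- Exclusion statements can be applied together. Item 12 is discretionary and not exhaustive, and 2.8 and 2.9 are headed as key criteria. A patient with an MI 2 years ago is barred by 10.4 and 10.5.1, and nothing in 2.9 requires admission. This is a conflict of text, not proof that the stricter rules are ignored.
- The 6-month sentence does not name MI or surgery. It covers a class, and a 6-month MI window is inferred from the list earlier in that section. The inference is fair but is not stated.
- Section 10 carries traces of an older design: ages 50-80 in 10.5, ages 60-80 in 10.5.1, and a later celecoxib phase in 10.4. Section 10.5.2 calls the previous criteria and procedures, ABPM above all, too demanding after 2 patients enrolled in 2 years. The lifetime rule may be a remnant, so it should not be assumed to be the intended one.
- Other safeguards exist: the EKG, beta-blocker and NSAID exclusions, investigator discretion on safety, dose review by the investigator, the medical monitor and the DSMB. Section 10.4 adds "We will perform the EKG and cardiac risk assessment following the completion of the initial phase of the study", but that check precedes open-label celecoxib; participants randomised to celecoxib have already been exposed by then. None of these settles the history rule or supplies the missing criterion.
- Baseline office pressure could serve as a substitute comparator. The plan does not say so, and office readings give no nighttime mean.

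The claim that the *initial strategy* wording makes the two-part rule mere history does not stand, because 10.5.2 explicitly reapplies the same criteria to the follow-up recording.

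**Conclusion.** The point holds as a defect of specification in two parts. The cardiovascular-history exclusion and the Framingham limit are stated inconsistently, so the minimal-risk statement in 10.4 relies in part on exclusions that the eligibility list does not require. It also relies on blood-pressure and gastrointestinal monitoring, the DSMB and the IND, and those are unaffected. Separately, the stopping rule cannot be decided in one defined situation: no baseline ABPM and a follow-up daytime mean systolic of 150 mmHg or more. This second part is the more pressing, because no operative rule exists there.

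A reader might infer more, and the documents do not support it:

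- *That patients are cleared to enrol once 4 weeks have passed.* Item 12 is judged case by case and gives no such permission.
- *That the excess risk is known.* Section 10.5.1 prints 8.3% and 1.9% for celecoxib patients with and without past events, a ratio of 8.3/1.9 = 4.4. The text labels these percentages hazard ratios, compares only celecoxib users and so may reflect prognosis, and itself says events are too few to estimate short-term risk.
- *That a handful of participants will hit the gap.* Applying the 7-17% of above-average responses in 10.5.2 to 50 celecoxib participants gives 3.5 to 8.5. That range uses a different definition (a 20 mmHg rise and systolic above 140 mmHg) in older subjects, while this trial enrols from age 18. It says nothing about who lacks a baseline.

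No count of affected patients can be derived.

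**What to change.** (a) Add to 10.5.2: *If no baseline ABPM exists, a follow-up daytime mean systolic of at least 150 mmHg alone leads to discontinuation of celecoxib/placebo.* The cost is that a few more participants stop than under the two-part rule; the participant in the example above would stop instead of continuing.

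(b) State one cardiovascular-history rule in 2.9 item 12 and make 10.1.6, 10.4 and 10.5.1 match it, saying that hypertension controlled to 150/90 mmHg or below stays eligible. The direction is the sponsor's choice. Adopting the lifetime MI and cardiac-surgery exclusion in 2.9 costs some recruitment. Keeping the rule in 2.9 and correcting 10.1.6, 10.4 and 10.5.1, including the minimal-risk statement, costs none.

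(c) Either add a Framingham score below 13 to the additional criteria for depressed participants only, since controls receive no study drug, or remove it from 10.5.1 as a stated mitigation. Adding it would mainly lose older patients, given the pilot means.

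All three are wording amendments with an updated eligibility checklist.

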### **1.1 *Introduction***

Major depression (MDD) is a cause of disability worldwide, but the etiology of MDD remains unclear. An emerging concept is that inflammation may have relevance, especially in MDD. We have data supporting increased inflammatory cytokines in MDD compared with controls that are associated with decreased hippocampus and amygdala volumes. MDD also had impairment in neuropsychological function in episodic memory, executive function, decreased hippocampus and amygdala resting state functional connectivity. Antidepressant treatment improved IL-6 levels, neuropsychological testing and resting state connectivity.

We will recruit patients with MDD (n = 100) and controls (n = 50) to characterize immune function, brain structure and connectivity and neuropsychological function. Using the Hospital of University of Pennsylvania's Pepper Lab we will measure participants' c-reactive protein (CRP) levels, and stratify participants according to CRP level (i.e. high (CRP  $\geq$ 3) and low (CRP  $<$ 3)). All participants with MDD (n=100), will receive a selective serotonin reuptake inhibitor (SSRI) antidepressant and we will randomize them to SSRI plus placebo (n $\leq$ 50) or SSRI + celecoxib (n $\leq$ 50). We will assess participants pre- and post-treatment with peripheral and central cytokine levels, neuropsychological tests and brain resting state functional connectivity.

Hypothesis 1: a) Compared with matched controls, MDD will have abnormalities in peripheral and inflammatory cytokines, neuropsychological function, hippocampal, amygdala and prefrontal cortex (PFC) structure and functional connectivity; b) Peripheral/central inflammatory cytokine levels will be associated with volume loss in hippocampus and amygdala; and c) Cumulative duration of depression will correlate with volume loss in hippocampus, amygdala, and PFC. d) Across the lifespan there will be an age effect interaction with depression.

Hypothesis 2: a) Once subjects have completed the antidepressant treatment, they will have greater normalization of IL-6 and IL-10, greater improvements in memory, executive function, and in resting state functional connectivity compared to their baseline measures; b) Improvement in clinical depressive scores will correlate with normalization of inflammatory cytokines; c) Those randomized to the addition of celecoxib (vs placebo) will have additive improvements in cytokines, resting state functional connectivity and depression scores.

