#### **5.6 Protocol Non-Conform Drugs**

Urine may be used to assess intake of protocol non-conform drugs by means of the Rapid Detect 10 Panel Test Dip Card, Rapid Detect, Inc., [name] (or similar). The drug screen includes for example Amphetamines (AMP), cocaine (COC), Tetrahydrocannabinol (THC), methamphetamine (mAMP), opiates (OPI), Phencyclidine (PCP), benzodiazepines (BZO), tricyclic antidepressants (TCA), barbiturates (BAR), and methadone (MTD). This can be done both prospectively and retrospectively.

CONFIDENTIAL

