### **5.11 Urinary Prostaglandin Metabolites**

If urine samples are available, drug effects of celecoxib are easily quantified by measuring prostaglandin metabolites in the spot urine collections. Spot urine collections will be stored at -80°C until analysis. The urinary prostacyclin metabolite, 2,3-dinor-6-keto-PGF1α (**PGI-M**), the thromboxane metabolite, 11-dehydro-thromboxane B2 (**TxB-M**), possibly also including 2,3-dinor-TxB-M and the prostaglandin metabolites 7α-hydroxy-5,11-diketotetranorprostane-1,16-dioic acid (**PGE-M**) and 11β-dihydroxy-15-oxo-2,3,18,19-tetranorprost-5-ene-1,20-dioic acid (**PGD-M**) will be quantified by LC/MS/MS. These assays are routinely performed in the Institute for Translational Medicine and Therapeutics' mass spectrometry laboratories with inter- and intra-assay variabilities of 4-8%.

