## 12 Appendix

### 12.1 Study Flow-Chart

Procedures conducted with all participants				
Procedure	Phone Screen	In-person Screen	Baseline	Week 6
Informed Consent		X (Initial screening consent)	X (Full study consent)	X
Verbal Consent	X			
Screen, History (include GI/bleeding risks)	X			X
Screen, History, SCID, MADRS, HAMD, CGI, MOCA		X		
EKG		X		X
PE , Laboratory tests, including IL-6, IL-10, CBC with diff;		X	X	X
MRI; structural and functional			X	X
Lifetime depression, PSS, LES score			X	
Framingham VRF, CIRS-G, QOL		X		X
Neuropsychological tests (COWA, Trails A & B, WLMT, Digits Forward, Digits Backward, Digits Ascending, MMSE, Logical Memory, Digit Symbol, Benton Visual Retention, Shipley Vocabulary, Boston Naming, CogState)			X	X

\*.

CONFIDENTIAL

This material is the property of the University of Pennsylvania.

Additional procedures conducted with depressed participants initially randomized to celecoxib:					
Procedure	Study Visits				
	Baseline	Wk 1	Wk 2	Wk 4	Wk 6
Concomitant Medications	X	X	X	X	X
Drug Dispensed Escitalopram + celecoxib or escitalopram + placebo (weeks 0-6)	X	X	X	X	X
Psychiatrist evaluation, depression scales, Vital Signs (including optional urine samples at baseline, week 1 or 2, and 6; triplicate in-office BP weekly and monitor GI-pain/bleeding for safety ),AEs, SAEs	X	X	X	X	X
PE (Lab tests including IL-6, IL-10, CBC with diff)	X	X	X	X	X
Liver function test & GI/bleeding risks	X		X		
Actigraphy (1 consecutive day minimum, optional longer),		X	X	X	
Optional Stool Sample	X		X		X
Optional Saliva samples	X	X	X	X	X
Safety (ABPM, FOBT and/or hematocrit levels)	X		X		
Safety (24-hour dietary recall, optional counseling on sodium-deplete diet)	X	X			

CONFIDENTIAL

This material is the property of the University of Pennsylvania.

	Additional procedures conducted with depressed participants initially randomized to placebo:									
	Procedure			Phase 1			Open Label Phase			
	Baseline	Wk 1	Wk 2	Wk 4	Wk 6	Wk 1	Wk 2	Wk 4	Wk 6	
Concomitant Medications	X									
Drug Dispensed Escitalopram + celecoxib or escitalopram + placebo (weeks 0-6) (Open label- Escitalopram + celecoxib)	X	X	X	X	X	X	X	X	X	
Psychiatric evaluation, depression scales, Vital Signs (including optional urine samples at baseline, week 1 or 2, and 6; triplicate in-office BP weekly and monitor GI-pain/bleeding for safety ),AEs, SAEs	X	X	X	X	X	X	X	X	X	
Liver function test & GI/bleeding risks	X		X				X			
Actigraphy	X	X	X	X	X	X	X	X	X	
Optional Saliva samples	X	X	X	X	X	X	X	X	X	

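### NSAID and steroid use is restricted only at entry, and later medication is charted only for the celecoxib arm, so placebo-arm use could dilute the contrast without systematic capture

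*Combined protocol and SAP*

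**What the plan says.** The randomised question is whether celecoxib adds to escitalopram. Section 1.1 predicts: "Those randomized to the addition of celecoxib (vs placebo) will have additive improvements in cytokines", and likewise in connectivity and depression scores. Section 2.1 makes IL-6 the primary cytokine measure.

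Other anti-inflammatory drugs are restricted in one eligibility rule, item 18 of section 2.9, which excludes "Current treatment with psychotropic drugs or drugs that affect the CNS such as beta-blockers, mood stabilizers, antipsychotics, steroids or non-steroidal anti-inflammatory medications". The same item admits participants only if "they have been off all psychotropics for at least 3 weeks" (longer for fluoxetine). It names no interval for NSAIDs or steroids.

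After entry, the relevant text is as follows:

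- **Flow chart, section 12.1.** There are two schedules, headed "Additional procedures conducted with depressed participants initially randomized to celecoxib" and "Additional procedures conducted with depressed participants initially randomized to placebo". The row "Concomitant Medications" is marked at baseline and weeks 1, 2, 4 and 6 in the first. In the second, as extracted, it carries one mark, at baseline, and none in the open-label columns.
- **Section 5.6.** "Urine may be used to assess intake of protocol non-conform drugs", which is optional. The ten drugs or classes named include no NSAID and no steroid.
- **Section 5.11.** "drug effects of celecoxib are easily quantified by measuring prostaglandin metabolites in the spot urine collections", but only where urine is available, and the flow chart makes urine optional.
- **Section 6.1.** The planned sensitivity analysis on concomitant drugs covers statins and ARBs only.
- **Section 10.5.2.** Patients with an above-average pressure response are to be advised to be careful with NSAIDs. This is safety advice to a subgroup, not a rule on study conduct.

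**The concern.** On the protocol's own reasoning, an NSAID taken by a placebo participant supplies part of the treatment under test. Section 10.5 describes NSAIDs as COX inhibitors. Section 1.2 supports the trial with a meta-analysis in which anti-inflammatory treatment, NSAIDs included, lowered depressive symptoms. Every randomised patient takes escitalopram, and section 10.1.5 lists headache among its side effects. That some patients would treat a headache with an NSAID is a supposition, since the documents give no usage rate.

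At stake is a real celecoxib effect that looks smaller than it is, in a trial that could not tell afterwards whether contamination was the reason. In the open-label phase, the former placebo participants take celecoxib with no charted medication record against which to read a bleed or a rise in blood pressure.

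**Working it through.** **Inputs.** Section 2.7, Hypothesis 2a: IL-6 difference 2.1, SD 3.6, 50 per group, two-sided 5%, 80% power; preliminary difference 2.7 (SD 3.6). Two quantities are not in the documents and are assumed: c, the share of placebo participants sampled on an NSAID (10%, 20%, 30%), and r, the NSAID effect relative to celecoxib (1 or 0.5).

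**Step 1: reproduce the plan's figure.** n per group = 2(1.960 + 0.842)² × (3.6/2.1)² = 46.1, so 47; the exact t calculation gives 48. With 50 per group the noncentrality is 2.1/(3.6 × √(2/50)) = 2.1/0.72 = 2.92, and power with 98 degrees of freedom is 82.3%. The stated 80% is therefore reproduced, slightly on the safe side.

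**Step 2: dilute the difference.** Observed difference = δ × (1 − c × r), with the SD held at 3.6 and no added effect of NSAIDs in the celecoxib arm. Power is from the exact t-test, 50 per arm.

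| Placebo-arm use c | δ = 2.1, r = 1 | δ = 2.1, r = 0.5 | δ = 2.7, r = 1 |
|---|---|---|---|
| 0 | 2.10, 82% | 2.10, 82% | 2.70, 96% |
| 10% | 1.89, 74% | 1.995, 78% | 2.43, 92% |
| 20% | 1.68, 64% | 1.89, 74% | 2.16, 84% |
| 30% | 1.47, 53% | 1.785, 69% | 1.89, 74% |

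For example, at c = 20% and r = 1: 2.1 × 0.8 = 1.68 and noncentrality 1.68/0.72 = 2.33, giving 64%. In the first power column, restoring 80% would take 57, 73 or 95 per arm at 10%, 20% or 30% use (normal approximation).

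**Step 3: set the two schedules against the blinding.** Section 4.6 blinds the PI and all but one member of the team. In weeks 0 to 6 blinded staff cannot take a medication history in one arm and omit it in the other, because they do not know the arm. The two rows therefore cannot both be carried out as charted.

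**The case against.** - **The table may be damaged.** The placebo schedule's header is scrambled in the extracted text, and a merged cell or lost marks would look the same as a single mark. The two schedules also differ on stool samples, laboratory tests and actigraphy, which suggests loose drafting rather than an intended rule. This stands as a caution: the row must be checked against the source PDF. Other rows of that table keep their marks across visits, and the gaps in the on-study text and the analysis remain even if this row is an artefact.
- **Blinding would force equal recording.** It may in practice, but it makes the chart unworkable; it does not make it correct. A reader might infer that the team intends to record medication in one arm only. The documents do not show that intent.
- **Some recording exists.** Section 7.2 has adverse events sought at each contact and recorded with actions taken, and section 7.4.1 mentions concomitant medication in SAE follow-up reports. A headache treated with an NSAID might surface there. So it would be too strong to say that placebo-arm use could never be found, but this capture is incidental.
- **The numbers are a proxy.** Section 2.7 compares medicated with nonmedicated subjects, whereas every randomised patient receives an SSRI. Neither 2.1 nor 2.7 is a celecoxib-placebo effect, and occasional NSAID use may not match six weeks of daily celecoxib. This stands, which is why several scenarios are shown.
- **The washout wording.** A reader might infer that NSAID use just before the screening CRP biases the arm comparison. It does not: such use precedes randomisation and is balanced between arms in expectation. At most it misplaces a participant's CRP stratum.

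**Conclusion.** The point holds as one of dilution and missing systematic capture. Item 18 governs entry only, no text says how NSAID or steroid use is handled after entry, no planned analysis names these drugs, and the charted recording differs by arm.

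A reader might go further and infer that placebo-arm NSAID use could erase the contrast. The figures do not support that. At 10% to 30% use, 70% to 90% of the difference remains even if an NSAID equals celecoxib, and it reaches zero only at c = 100% with r = 1. Under this model the bias is towards the null: a loss of power, not a false positive.

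The loss at 50 per arm ranges from 4 percentage points (96% to 92%: difference 2.7, 10% use; likewise 82% to 78%: difference 2.1, half effect, 10% use) to about 30 (82% to 53%: difference 2.1, full effect, 30% use). These are illustrations resting on an assumed usage rate, an assumed relative effect and a proxy difference. The case for acting is that the remedy is cheap and that use not recorded at the time cannot be reliably recovered later.

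**What to change.** 1. Check the placebo row against the source PDF and reconcile the two schedules in section 12.1. Concomitant medication should be recorded at the same visits in both arms (baseline and weeks 1, 2, 4 and 6) and at every open-label visit. Ask specifically about NSAIDs, aspirin and steroids, with the date of last intake.
2. Reconcile item 18 with the on-study period. The sponsor's clinicians should decide, and the protocol should state, how NSAID and steroid use before sampling and during the study is handled. This review proposes no clinical rule.
3. Add NSAID and steroid use to the statin and ARB sensitivity analysis in section 6.1, for IL-6 and MADRS. Keep the full randomised comparison as the main analysis, and state that excluding or adjusting for use after randomisation is not protected by randomisation. Where optional urine exists, prostaglandin metabolites assayed blind to arm can support this analysis.

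The cost is one CRF question at existing visits and one extra analysis. Urine coverage will be partial.
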